7.1.7. Protocol Deviations Because of an Adverse Event

If a patient experiences an adverse event or medical emergency, the investigator should take the actions necessary to ensure patient safety. After the event has stabilized; treatment has been administered or both, the investigator or other physician in attendance must contact the physician identified in the Clinical Study Personnel Contact Information section of this protocol as soon as possible to discuss the situation. The investigator, in consultation with the sponsor, will decide whether the patient should continue to participate in the study.

7.2. Adverse Device Effects

An adverse device effect is an adverse event related to the use of an investigational medical device or a combination product. This includes adverse events resulting from insufficient or inadequate instructions for use, deployment, implantation, installation, operation, or any malfunction of the investigational medical device, including any event resulting from user error or from intentional misuse of the investigational medical device.

7.2.1. Adverse Device Effect Reporting

Adverse device effects ([Figure 2](#)) must be recorded on both the source documentation and the CRF.

All adverse device effects shall be reviewed by the investigator, the medical monitor, and the sponsor. The investigator and sponsor will record all relevant information regarding every adverse device effect/serious adverse device effect and device deficiency and will categorize each as guided in Section 7.2.

The investigator should make an initial determination whether the adverse event may be related to a device deficiency (Section 7.1.4).

Adverse device effects and device deficiencies will be listed in the clinical study report (CSR).

7.2.2. Serious Adverse Device Effects

A serious adverse device effect is an adverse device effect that has resulted in any of the consequences characteristic of a serious adverse event (Section 7.1.5.1).

7.2.2.1. Serious Adverse Device Effect Reporting

[figure not shown]
The investigator will report to the sponsor, without unjustified delay, all serious adverse device effects (within 24 hours); this information shall be promptly followed by detailed written reports as described below.

The process and contact details for serious adverse device effect reporting are the same as for serious adverse event reporting provided in Section 7.1.5.3.

Events shall be reported to the IEC/IRB by the investigator and to the regulatory authorities by the sponsor using the appropriate form according to national and local regulations.

The investigator should make an initial determination whether the serious adverse event may be related to a device deficiency.

Figure 2: Decision Tree for Adverse Events and Adverse Device Effects Classification

AE=adverse event; ADE=adverse device effect; CRF=case report form; IEC=Independent Ethics Committee; IRB=Institutional Review Board; SADE=serious adverse device effect; SAE=serious adverse event.

7.3. Pregnancy

Any female patient becoming pregnant during the screening period will be considered a screen failure and will not be allowed to rescreen.

Any female patient becoming pregnant during the study will discontinue IMP.

All pregnancies of women participating in the study and female partners of men participating in the study, if applicable, that occur during the study, or within 5 half-lives (~10 weeks) of the last IMP administration, are to be reported immediately to the individual identified in the Clinical Study Personnel Contact Information section of this protocol, and the investigator must provide the sponsor (LSO/CRO) with the completed pregnancy form. The process for reporting a pregnancy is the same as that for reporting a serious adverse event but using the pregnancy form (Section 7.1.5.3).

All female patients and female partners of men participating in the study (female partners of men participating in the study who become pregnant will be asked to sign an ICF) who become pregnant will be monitored for the outcome of the pregnancy (including spontaneous, elective, or voluntary abortion). If the pregnancy continues to term, the outcome (health of the infant up to 8 weeks of age), including details of birth and presence or absence of any birth defect, congenital abnormalities, or maternal and newborn complications, will be reported to the sponsor. Any complication of pregnancy during the study and any complication of pregnancy that the investigator becomes aware of after withdrawal from the study will be reported as an adverse event or serious adverse event, as appropriate.

If the pregnancy in the woman participating in the study and/or the female partners of men participating in the study does not continue to term, 1 of the following actions will be taken:

- For a spontaneous abortion, report as a serious adverse event.
- For an elective abortion due to developmental anomalies, report as a serious adverse event.
- For an elective abortion **not** due to developmental anomalies, report on the pregnancy form; do not report as an adverse event.

7.4. Medication Error and Special Situations Related to the Investigational Medicinal Products

Any administration of IMP that is not in accordance with the study protocol should be reported in the patients' source documents, regardless of whether or not an adverse event occurs as a result.

The following are types of medication errors and special situations:

2. Medication error: Any unintentional error in the prescribing, dispensing, or administration of a medicinal product while in the control of the healthcare professional, patient, or consumer.
3. Overdose: Administration of a quantity of a medicinal product given per administration or cumulatively which is above the maximum recommended dose according to the authorized product information/study protocol. Clinical judgment should always be

applied. Any dose of IMP (whether the test IMP or placebo IMP), whether taken intentionally or unintentionally, in excess of that prescribed must be immediately reported to the sponsor.

4. Misuse: Situations where the IMP is intentionally and inappropriately used not in accordance with the authorized product information/study protocol.
5. Abuse: Persistent or sporadic, intentional excessive use of IMP which is accompanied by harmful physical or psychological effects.
6. Off-label use: Situations where an IMP is intentionally used for a medical purpose not in accordance with the authorized product information/study protocol.
7. Occupational exposure: Exposure to an IMP, as a result of one's professional or non-professional occupation.
8. Breastfeeding: Suspected adverse reactions which occur in infants following exposure to a medicinal product from breast milk.

7.5. Clinical Laboratory Tests

All clinical laboratory test results outside of the reference range will be judged by the investigator as belonging to one of the following categories:

- abnormal and not clinically significant
- abnormal and clinically significant

A laboratory test result that is judged by the investigator as clinically significant will be recorded both on the source documentation and the CRF as an adverse event, and monitored as described in Section 7.1.2. A laboratory or diagnostic test abnormality (once confirmed by repeated testing) that results in the withdrawal of the patient from the study; the temporary or permanent withdrawal of IMP or medical treatment, or further diagnostic work-up may be considered adverse events. If further diagnostic work-up of abnormal laboratory result leads to the investigator concluding that the initial abnormality was not clinically significant, it is at the investigator's discretion whether or not the laboratory result triggering the work-up is an adverse event. (Note: Abnormal laboratory or diagnostic test results at the screening visit(s) that preclude a patient from entering the study or receiving IMP are not considered adverse events.)

Table 7: Clinical Laboratory Tests

Serum Chemistry	Hematology and Coagulation	Urinalysis
Calcium	Hemoglobin	Protein
Phosphate	Hematocrit	Glucose
Sodium	Erythrocytes	Ketones
Potassium	Platelets	Hemoglobin
Chloride	Leucocytes (including differential count, presented in absolute values and percentages)	pH
Creatinine	– Neutrophils	Specific gravity
Glucose	– Lymphocytes	Microscopic tests
Blood urea nitrogen (BUN)	– Eosinophils	– Bacteria
Urate	– Monocytes	– Erythrocytes
Alanine aminotransferase (ALT)	– Basophils	– Leucocytes
Aspartate aminotransferase (AST)	– Lymphocytes atypical	– Crystals
Lactate dehydrogenase (LDH)	Prothrombin International Normalized Ratio (INR)	– Casts
Gamma-glutamyl transpeptidase (GGT)		
Alkaline phosphatase		
Protein		
Albumin		
Bilirubin		
Direct bilirubin		

7.5.1. Serum Chemistry, Hematology, and Urinalysis

Clinical laboratory tests (serum chemistry, hematology and coagulation, urinalysis) will be performed at the time points detailed in [Table 2](#) (screening and run-in), [Table 3](#) (treatment period), and [Table 4](#) (follow-up). Tests can be performed in either a fasting or non-fasting state. Clinical laboratory tests will be performed using the central laboratory. Details of laboratories to be used in the study are provided in [Appendix A](#).

7.5.2. Other Clinical Laboratory Tests

At screening, patients will be tested for hepatitis B surface antigen (HBsAg), antibodies to hepatitis C virus (HCV), human immunodeficiency virus (HIV) types 1 or 2, and TB test (QuantiFERON[®] TB Gold Test). Patients with confirmed positive results will not be eligible to participate in the study.

If the QuantiFERON[®] TB Gold Test is negative at screening, then the patient may proceed in the screening period. However, if the QuantiFERON[®] TB Gold Test is deemed by the principal investigator to be a false positive at screening, then a second sample should be drawn and the following steps taken:

- If the second QuantiFERON[®] TB Gold Test is positive (ie, results match the first test), then the patient will be a screen failure.
- If the second QuantiFERON[®] TB Gold Test is negative (ie, results do not match the first test), then a third sample should be drawn.

- If the third QuantiFERON[®] TB Gold Test is positive (ie, results match the first test), then the patient will be a screen failure.
- If the third QuantiFERON[®] TB Gold Test is negative (ie, results match the second test), then the patient may proceed in the screening period.
- Note that sites may choose to split the second and third samples and send one to the central laboratory and one to a local laboratory. However, the local laboratory result may not be used for decision making.

COVID-19 testing will be available at the central laboratory. Locally performed COVID-19 testing results will also be accepted.

7.5.2.1. Human Chorionic Gonadotropin Tests

Human chorionic gonadotropin (HCG) tests in serum and in urine will be performed for women of childbearing potential at the time points detailed in [Table 2](#) (screening and run-in), [Table 3](#) (treatment period), and [Table 4](#) (follow-up).

7.5.2.2. Follicle Stimulating Hormone

At screening, women who have been amenorrheic for at least 1 year without an alternative medical cause will have a serum follicle stimulating hormone (FSH) assessment to confirm postmenopausal status (an increased concentration of FSH of more than 35 IU/L in women not using hormonal contraception or hormonal replacement therapy).

7.6. Local Tolerability

Local tolerability assessments should be performed after each administration of IMP ([Table 3](#)) and include administration site findings and pain. Administration site findings (erythema, ecchymosis, induration, tenderness, warmth, and swelling) will be assessed using the scales provided in [Table 8](#). Pain at the administration site will be reported using a standardized 11-point pain intensity numerical response scale (NRS-11) where 0 is “No pain” and 10 is “Worst possible pain”. Patients will be asked to respond to the following question: “How much pain do you feel at the drug injection site?”

Both administration site findings and pain will be assessed 1 hour after the completion of IMP administration. Additionally after the loading dose and first maintenance dose, assessments will also be performed 2 hours after the completion of administration. Allowed time windows for the local tolerability assessments are ± 15 minutes.

Severity of local tolerability symptoms should be assessed as described in [Table 8](#). The surface diameter in millimeters should be recorded and erythema, induration, and ecchymosis at the administration site will be graded according to the diameter measurements: Absent, 5 mm to ≤ 50 mm (mild), >50 to ≤ 100 mm (moderate), and >100 mm (severe). Erythema, ecchymosis, and induration under 5 mm in diameter should be assessed as absent. Care should be taken to avoid pressuring or squeezing the administration site while assessing induration via careful superficial palpation.

In the case that findings do not resolve while the patient remains at the study center, additional evaluation should take place thereafter at each visit until resolution occurs. Administration sites

may be photographed, including between visits to the study center, to provide visual representation in addition to comments in the source documents. Any features that could be used to identify the patient will not be captured on the photograph. Appropriate treatment for administration site finding or pain may be provided if necessary, in which case such treatments must be recorded as concomitant medication(s).

Table 8: Administration Site Finding Severity Assessment

Test	Response
Erythema	- Absent - Erythema surface diameter 5 mm to ≤50 mm (mild) - Erythema surface diameter >50 to ≤100 mm (moderate) - Erythema surface diameter >100 mm (severe)
Ecchymosis	- Absent - Ecchymosis surface diameter 5 mm to ≤50 mm (mild) - Ecchymosis surface diameter >50 to ≤100 mm (moderate) - Ecchymosis surface diameter >100 mm (severe)
Induration	- Absent - Induration surface diameter 5 mm to ≤50 mm (mild) - Induration surface diameter >50 to ≤100 mm (moderate) - Induration surface diameter >100 mm (severe)
Tenderness Warmth Swelling	- None - Mild - Moderate - Severe

Administration site findings described in [Table 8](#) and administration site pain will not be captured as adverse events. Administration site findings with characteristics that are not described in [Table 8](#) or this section (eg, lipoatrophy, necrosis, abscess) or fulfill seriousness criteria must be recorded and reported as specified in [Section 7.1.2](#) and [Section 7.1.5](#).

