7.1.6. Protocol-Defined Adverse Events of Special Interest

For purposes of this protocol, the following are considered protocol-defined adverse events of special interest:

- systemic severe reactions (including anaphylaxis)
- opportunistic infections
- malignancies (including non-melanoma skin cancer)

- administration site reactions

The process of reporting the above mentioned adverse events, except for administration site reactions, is the same as that for reporting serious adverse events (Section 7.1.5.3). Protocol-defined adverse events of special interest should be reported to GPSP regardless of seriousness or causality assessment, according to the criteria outlined in Section 7.1.5.1.

Administration site reactions will be evaluated and reported as described in Section 7.6.

In the event of suspected anaphylaxis while the patient is at the site, vital signs, including blood pressure, oxygen saturation, and respiration rate, should be measured. FEV₁ and PEF measurements should be obtained if it is safe to do so in the investigator's opinion. Blood samples to test TEV-48574 serum concentration, ADA, and free and total serum TL1A levels should be collected if possible. Collection of blood samples to test tryptase and/or histamine levels are encouraged if available locally at the time of the suspected hypersensitivity event. Other assessments may be performed at the discretion of the investigator. As a precaution, each site should have a resuscitation medication/equipment nearby. In addition, information about all suspected anaphylaxis and hypersensitivity events will be recorded on the Suspected Anaphylaxis CRF, which is based on the 2006 Joint NIAID/FAAN Second Symposium on Anaphylaxis (Sampson et al, 2006).

A list of opportunistic infections is included in [Appendix I](#).

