### **8.3. Adverse Events**

Adverse events will be recorded from time informed consent is obtained through the end of study participation.

All adverse events will be coded using MedDRA. Each patient will be counted only once in each preferred term or SOC category for the analyses of safety. Summaries will include treatment-emergent adverse events which are defined as adverse events occurring at or after the first dose of the IMP through the end of the follow-up visit. Listings will include all adverse events recorded.

Summaries will be presented for all adverse events (overall and by severity), adverse events determined by the investigator to be related to test IMP (defined as related or with missing relationship) (overall and by severity), adverse events determined by the investigator to be related to the medical device, or the study inhaler (defined as related or with missing relationship), serious adverse events, and adverse events causing drug withdrawal or discontinuation from the study. Adverse events with the missing flag indicating serious will be excluded from the summary of serious adverse events but included in the summary of non-serious adverse events.

Summaries for clinical asthma exacerbation related adverse events, loss of asthma control related adverse events, injection site reaction adverse events, protocol-defined adverse events of special interest (PDAESI), PDAESI require completion of suspected anaphylaxis will also be presented.

Listings for deaths, serious adverse events, adverse events leading to drug withdrawn or the study discontinuation, clinical asthma exacerbation related adverse events, loss of asthma control

related adverse events, injection site reaction adverse events, PDAESI, and PDAESI require completion of suspected anaphylaxis, adverse event required concomitant or additional treatment will be presented. In addition, listings for MedDRA dictionary terms for adverse event descriptions and adverse event preferred terms by patient number and treatment group will be presented.

Adverse events for patients who did not meet screening criteria will be listed.

In additional, adverse events and serious adverse events occurred during the 10 weeks period after the last dose of IMP will be summarized using descriptive statistics. These adverse events will be presented in a patient listing as well. Injection Site Assessments

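### Non-serious, common-type site reactions that start after the 1- or 2-hour check and clear before the next visit have no planned capture, although site reactions are an event of special interest

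*Protocol*

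**What the plan says.** Protocol 7.6 sets the schedule: "Both administration site findings and pain will be assessed 1 hour after the completion of IMP administration". It adds: "Additionally after the loading dose and first maintenance dose, assessments will also be performed 2 hours after the completion of administration". The permitted window is plus or minus 15 minutes. Later follow-up, which continues for as long as the finding lasts, is conditional: "In the case that findings do not resolve while the patient remains at the study center, additional evaluation should take place thereafter at each visit".

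The same section then separates these data from adverse events: findings of the Table 8 kinds "and administration site pain will not be captured as adverse events". Two exceptions follow. Findings of a kind not described there (lipoatrophy, necrosis and abscess are the examples) and findings that meet seriousness criteria must be recorded and reported.

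Protocol 7.1.6 lists administration site reactions among the protocol-defined adverse events of special interest (PDAESI). It takes them out of the expedited route used for the others: "Administration site reactions will be evaluated and reported as described in" Section 7.6.

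On analysis, SAP 8.3 plans adverse-event summaries for "injection site reaction adverse events, protocol-defined adverse events of special interest (PDAESI"). Under its injection-site paragraph it also summarizes the Table 8 findings and the NRS-11 pain score by visit, with the worst pain score overall. Local tolerability is a listed safety endpoint in Protocol 9.5.3 and SAP 1.3.

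**The concern.** A dedicated graded form for site findings, in place of duplicate adverse-event entries, is a sensible design. It works when the form sees the finding. Here the exemption is worded by type of finding, not by whether the form recorded it. A reaction that develops at home is thus exempt from adverse-event recording although the form never saw it.

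Two things are at stake. First, the trial could not describe delayed, transient site reactions to a repeated subcutaneous regimen, in either arm. Second, the PDAESI and site-reaction adverse-event tables would be sparse because of a recording rule, and nothing in the SAP tells the reader so.

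**Working it through.** No power or event-rate calculation applies, and the plan states no figure to reproduce. The check follows one event through the text, with simple arithmetic for the schedule.

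**Schedule (Protocol 7.6 and Table 3).** There are eight doses, at visits 1 to 4 and 6 to 9, two weeks apart.
- Scheduled assessments: 2 × 2 + 6 × 1 = 10.
- Latest permitted check: 2 h + 15 min = 2 h 15 min after doses 1 and 2; 1 h + 15 min = 1 h 15 min after doses 3 to 8.
- Time to the next dosing or end-of-treatment visit: 14 days = 336 h.

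**The event.** Take a non-serious Table 8 finding, or pain, that starts after the latest check and has gone by the next visit.

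1. *Local tolerability assessment.* It was absent at the 1- or 2-hour check. The next assessment follows the next dose, when the finding has gone. After dose 8 the next visit is end of treatment, where Table 3 schedules no local tolerability assessment.
2. *Follow-up rule in 7.6.* This applies to findings not resolved while the patient is still at the center. A later onset does not trigger it.
3. *Other contacts.* The week 7 telephone visit has no site item. The e-diary reviews in the visit lists cover quick-relief use and nighttime awakenings.
4. *Adverse-event inquiry.* Protocol 7.1.2 requires an open question about adverse events at every contact, so the patient may well report the reaction. The same section requires every adverse event to be recorded whatever its severity. Section 7.6 removes this class. It sets no grade limit, so a diameter above 100 mm, which Table 8 calls severe, is removed too unless it is serious.
5. *Tables.* The event is absent from the by-visit site summaries and from the adverse-event and PDAESI summaries.

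**Consequence for the SAP 8.3 tables.**

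| Type of site event | Local tolerability tables | Site-reaction AE and PDAESI tables |
|---|---|---|
| Table 8 finding or pain, present at the 1- or 2-hour check, not serious | Yes | No, by 7.6 |
| Table 8 finding or pain, later onset, gone before the next visit, not serious | No | No, by 7.6 |
| Kind not described in 7.6 (eg, abscess) | Not a Table 8 item | Yes |
| Serious | If present at a check | Yes |

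The second row is the gap. The right-hand column shows that the adverse-event tables can hold only atypical or serious site events, while 7.1.6 names site reactions in general as of special interest.

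**The case against.** Much can be said for the plan.

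- **Immediate tolerability is covered.** Findings at 1 to 2 hours are graded, summarized by visit and listed, and unresolved ones are followed. This stands. A reader might infer that the trial collects nothing useful on site reactions; the documents do not support that.
- **Other traces exist.** Treatment of a site finding must be entered as concomitant medication, photographs between visits are allowed, and an unscheduled visit can include an examination. This stands, so it would be wrong to say that such an event leaves no record. But none of these grades or tabulates a reaction.
- **The safety committee is not confined to adverse-event tables.** Appendix B gives it all available safety data, and local tolerability is a safety endpoint. A reader might infer that the committee would be falsely reassured; the text does not show this. It would see the graded findings, and would lack only the class in the second row above.
- **The unobserved time says little.** A reader might divide 2 × 2.25 h + 6 × 1.25 h = 12 h by 8 × 336 h = 2,688 h and conclude that over 99% of reactions are missed. That ratio is clock time. The share missed depends on when reactions start and how long they last, which the visible text does not give.
- **Reasons may lie elsewhere.** The Phase 1 results and device details are largely redacted, and neither the CRF nor its completion guide is available. A rationale for the schedule, or a field for later-onset findings, could exist there. This lowers certainty about practice, but not about what 7.6 instructs.
- **Importance.** Proof of concept rests on loss of asthma control, the rule is the same in both blinded arms, and only non-serious transient events are affected. This stands and limits the severity.

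**Conclusion.** The gap is real but narrow. Read as written, 7.6 leaves one class of site event without planned capture as a tolerability finding or an adverse event: Table 8 findings or pain that are non-serious, begin after the 1-hour check (2-hour for doses 1 and 2), and resolve before the next visit. For that class planned capture is zero in both arms. Its frequency is unknown, and the documents allow no range.

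Separately, Protocol 7.1.6, Protocol 7.6 and SAP 8.3 do not fit together. Site reactions are of special interest, yet the planned adverse-event tables for them exclude the ordinary kinds.

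The conclusion assumes that sites follow 7.6 literally and that no unseen CRF instruction provides a place for later-onset reports. The primary analysis is not affected. I rate the point minor to moderate: a listed safety endpoint has a blind spot that the existing adverse-event inquiry could largely close.

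**What to change.** **Protocol 7.6.** Limit the adverse-event exemption to Table 8 findings and pain recorded on the local tolerability assessment. Site findings or pain that begin later and are reported at the adverse-event inquiry are recorded as adverse events with onset and end dates.

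**SAP 8.3.** Present the site-reaction PDAESI summary from two sources side by side: local tolerability records by Table 8 grade and NRS-11 score, and site-reaction adverse events by adverse-event severity. State what each table contains. Do not merge them into one worst grade. Table 8 grades erythema, ecchymosis and induration by measured diameter, Protocol 7.1.3 grades adverse events by limitation of activity, and a reaction recalled after it has resolved has no site-measured diameter.

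**Cost.** One sentence in 7.6, a CRF completion note and a revised SAP table; no new visit or procedure. More mild, non-serious adverse events will be recorded in both arms. The same erythema will also be a form entry if seen at the check and an adverse event if it starts later, which is why the two sources need to be shown and labelled separately.
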